6.3 Early withdrawal of subjects

Patients have the right to withdraw from the trial at any time and without giving any reason. If a patient withdraws from the trial, any and all information gathered prior to the withdrawal will be excluded in the analysis, no further data collection will occur. If a patient does not attend a planned follow-up appointment then two more attempts will be made to contact the patient regarding the study. If still no contact can be made then the patient is deemed lost to follow-up and any collected study data will be retained.

As mentioned in section 5.3, study subjects who subsequently require additional significant surgical intervention, primarily ligament reconstruction, will be withdrawn from the study.

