5.3 Consent and recruitment

Those eligible will be approached and provided with an information pack and consent form, which will be signed to indicate that informed consent has been given. Patients will be given ample time to consider taking part, more than 24 hours if they wish. The study will be first mentioned at an orthopaedics out-patient clinic visit. The direct healthcare professional will first approach a patient about the study, and after verbal consent by the patient the healthcare professional themselves or a member of the research team can go through the informed consent process.

Patients are also allowed to consent to taking part when first approached as long as the study has been discussed with the patient and they have been given time to read the patient information leaflet and opportunity to ask any questions that they may have. Participants will receive no incentives and consent will be regarded as a process and not a one-off event. Participants are free to withdraw from the study at any time without the need to give any reasons for withdrawal. Their standard of care will not be affected by either declining to participate in the study or withdrawing during participation. Data collected up to the date of withdrawal will be retained for analysis.

Participants will be randomised to either the treatment as usual (TaU) or the intervention group (Viscoseal) any time up until the day of surgery. Study subjects who subsequently require additional significant surgical intervention, primarily ligament reconstruction, will be withdrawn from the study.

The MRI sub-study will be offered to all patients consecutively, and this will be done until the 24 required patients for said sub-study have been recruited.

5.4 **Follow-up**

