Patients are in the study for a period of 26 weeks. Thereafter, the patient will be followed up as they would be in normal clinical practice. Two study follow-up visits are aligned to hospital/clinic visits and the other are done remotely. Baseline data can be collected on the day of surgery (prior the actual operation), and 48 hrs, 7 days, 14 days and 12 weeks post-surgery data can be collected when the patient attends for standard follow-up in the orthopaedics out-patient department. The data at week 26 falls outside these dates. In these instances, data can be collected over the phone, via e-mail or by mail (whichever is preferred by the patient – mail is by use of freepost, to avoid patients incurring any costs). The researcher will ask/phone/e-mail/mail the participant at each follow-up time point to check on any adverse event reporting, and if consented by the patient can

IRAS ref 272362 Page **12** of **30**

also send reminders to the participant regarding the completion of certain outcome data at the aforementioned follow-up time points.

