5.5 Outcome measures

5.5.1 **Primary outcome measures**

To determine the level of index leg related pain experienced at day 7 post-operation and to compare the average pain scores of patients in the control and Viscoseal arm respectively, through administration of 100 mm visual descriptor scale (VDS) for pain at rest.

The study is powered to detect the established minimal clinically important difference (MCID) of 15 mm on a 100 mm VDS pain.

5.5.2 **Secondary outcome measures**

All the outcome measures are summarised in Table 2.

Table 2. Overview of measurements

Weeks	-12 weeks to day of surgery	48 hours	7 days*	14 days*	12 weeks#	26 weeks~
VDS pain scale for knee (at rest)	Х	Х	Х	Х	Х	Х
VDS pain scale for knee (walking)	Χ				Х	Χ
McGill pain questionnaire (at rest)	Х	X	X	Х		
Limb girth measurement (index leg)	X			Х	Х	
Lysholm scale	Χ				Χ	X
WOMET tool	Χ				Χ	Χ
Use of analgesics / anti- inflammatories	Х	X	Χ	Х	X	X
Patient satisfaction questionnaire re surgery						Χ
MRI scan (sub-study; not all participants)						Х

^{*} Allowed to be up to 2 days early or late

IRAS ref 272362 Page **13** of **30**

[#] Allowed to be up to 2 weeks early or late

[~] Allowed to be up to 4 weeks early or late

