6. SUBJECTS

6.1 Anticipated number of research subjects

The sample size calculation does take into account a 10% patient attrition rate (withdrawal and loss to follow-up), since this involves a study with multiple time points for data collection up to 26 weeks. Patients will be recruited from the adult population routinely seen by the evaluating clinical staff members. The primary outcome measure is based on knee/leg (ie wound site) pain experienced 7-days post-surgery based on the VDS pain scale (with leg at rest). The hypothetical difference in pain perception, based on a previous publication involving meniscal repair and Viscoseal, is 15mm on a 100 mm scale which equates to a significant 'minimally clinically important difference' for pain (Kelly 2001; Lee et al 2003; Tashjian et al 2009).

The non-parametric two-sided Mann-Whitney u-test is applied because the data is ordinal; 80% power and 5% significance is also applied. A priori power calculations using GPower 3.1 software, result in the following sample size summarized in Table 3.

It involves a minimum total of **52 participants**, who undergo meniscal repair surgery. Randomised 1:1, therefore 26 patients per arm.

Table 3, Sample size calculation

	Mean pain score (mm) at 7 days post-op~	Standard Deviation (hypothetical)
Viscoseal	28	20
Standard care	43	20

IRAS ref 272362 Page **14** of **30**

	Power beta of 80%, Alpha p-value of 0.05, Effect size 0.75			
	Sample size required without any drop-out: 48 samples.			
	Sample size with 10% attrition rate included: 52			
	Total of 52 patients:			
	26 Patients to receive standard care			
	26 Patient to receive Viscoseal			
~Based on Thein et al. 2	010			

For the MRI imaging sub-study a total of 24 patients will be recruited, 12 controls and and 12 viscoseal patients. This is in line with guidelines on pilot studies [25].

The CONSORT guidelines require a statement on the number of patients assessed for eligibility (Schulz, Altman & Moher 2010). The number of patients screened but who did not meet the inclusion criteria or who declined to participate will be recorded, as will any patients who are lost to follow-up (Appendix 3).

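### Protocol sections 5.3 and 6.3 give opposite rules for data collected before withdrawal; followed as written, 6.3 would drop day-7 primary scores already recorded

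*Protocol*

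**What the plan says.** Three statements in the protocol govern what happens to data when a patient leaves.

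- Section 5.3, on participants who withdraw: "Data collected up to the date of withdrawal will be retained for analysis".
- Section 6.3, on the same event: "any and all information gathered prior to the withdrawal will be excluded in the analysis".
- Section 6.3, on patients who cannot be reached after repeated attempts: "the patient is deemed lost to follow-up and any collected study data will be retained".

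Sections 5.3 and 6.3 also provide for withdrawal by the study team. In the words of 6.3, "study subjects who subsequently require additional significant surgical intervention, primarily ligament reconstruction, will be withdrawn from the study". Neither section says which data rule then applies.

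The timing matters. Section 5.5.1 sets the primary outcome as pain at rest at day 7 ("To determine the level of index leg related pain experienced at day 7 post-operation"), while section 5.4 states "Patients are in the study for a period of 26 weeks". Section 6.1 adds: "The sample size calculation does take into account a 10% patient attrition rate (withdrawal and loss to follow-up").

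**The concern.** The two withdrawal rules cannot both be applied, and the choice decides who enters the primary analysis. If it stays open, it could be made after results are known.

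Under the 6.3 wording, a patient who gives a valid day-7 score and withdraws months later leaves the primary comparison. A patient with the same score who simply stops responding stays in. Membership of the analysis set would then depend on an event after randomisation. That departs from analysis of all randomised patients and can bias the comparison in either direction if withdrawal is related to pain or to knowledge of the allocation. The trial is single-blinded, so such a relation cannot be ruled out.

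The same exclusion could take these patients out of the descriptive safety overview in section 8.3. That overview counts returns to theatre or hospital, which patients withdrawn for further surgery may well contribute.

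**Working it through.** **1. The contradiction.** This needs no arithmetic.

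| How the patient leaves | Section 5.3 | Section 6.3 |
|---|---|---|
| Withdraws | earlier data kept for analysis | earlier data excluded from analysis |
| Lost to follow-up | not addressed | collected data kept |
| Withdrawn for further surgery | data rule not stated | data rule not stated |

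Both sections are current text. An analysis plan could not comply with both, so this is not a detail left to a later document.

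**2. Inputs for the size** (sections 5.5.1 and 6.1, Table 3). Difference 15 mm, SD 20 mm, so d = 15/20 = 0.75; alpha 0.05; 26 per arm; 10% attrition; two-sided test ("The non-parametric two-sided Mann-Whitney u-test is applied because the data is ordinal").

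**3. The plan's own figure.** Power is computed by the asymptotic relative efficiency method: noncentral t with n × 3/π per arm (normal parent). On the stated two-sided test, 80% power needs 31 per arm (62 in all), not 48. The figure of 48 is reproduced by the one-sided version (24 per arm, power 80.4%). For attrition, 48/0.9 = 53.3, i.e. 54 for equal arms, against the stated 52. This is a separate matter. It is noted because the two-sided power below starts under 80% for that reason, not because of the withdrawal rule.

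**4. Patients lost under 6.3.** 10% of 52 = 5.2. The allowance pools withdrawals, which 6.3 excludes, with losses to follow-up, which it keeps, and no split is given. The loss therefore runs from 0 (no attrition is a withdrawal after day 7) to about 5 (all of it is).

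**5. Power, two-sided Mann-Whitney, same method.**

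| Share of the 10% that is withdrawal after day 7 | n per arm | Power |
|---|---|---|
| none | 26 | 73.5% |
| half | 26 × 0.95 = 24.7 | 71.2% |
| all | 26 × 0.90 = 23.4 | 68.8% |

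The rows take all other day-7 scores as observed. The rule costs 0 to 73.5 − 68.8 = 4.7 points. In the last row 46.8 patients remain, just under the plan's own 48.

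**6. Shift in one arm's mean.** If a fraction p of an arm is excluded and those patients' mean lies δ from the arm mean, the mean of the rest moves by p × δ/(1 − p). The values of δ are assumptions.

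| p | δ = 10 mm | δ = 20 mm |
|---|---|---|
| 0.05 | 0.5 mm | 1.1 mm |
| 0.10 | 1.1 mm | 2.2 mm |
| 0.20 | 2.5 mm | 5.0 mm |

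The last row is an extreme. Since 5.2/26 = 0.20, it needs the whole 10% attrition to be withdrawal after day 7 and all of it in one arm.

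**7. The same extreme by simulation** (3,000 trials, normal data, 5 patients removed from the upper half of pain in one arm). A true 15 mm difference is estimated as about 11.3 mm if all five are controls and about 18.8 mm if all five are Viscoseal patients. With no true effect, the type I error is about 8-9% instead of 5%.

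**The case against.** **A drafting slip.** Replacing excluded by included in 6.3 would fit the preposition, the clause that follows on stopping further data collection, section 5.3, and the retention rule for patients lost to follow-up. This is plausible, and the sentence should not be taken as proof of a deliberate policy. It cannot be confirmed from the document, and the text needs correcting either way.

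**Deletion of data.** A reader might infer that 6.3 orders records to be destroyed. It does not; it excludes information from the analysis.

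**Loss of adverse events.** A reader might also infer that adverse events before withdrawal vanish. Section 7.3 requires every event to be reported, assessed and filed, with no exception for withdrawn patients. Only their place in the safety summary is at risk.

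**Size.** A loss of five patients, a 5-point fall in power and a 5 mm shift are upper ends, not expectations. The design already allows for 10% attrition, and similar exclusions in both arms would largely cancel in the difference. All of this stands, so the effect is given as a range starting at zero.

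**Remedy.** The leaflet and consent form are not at hand. Section 5.1 planned recruitment from January 2020 and this version dates from May 2021, so participants may already have consented under one wording or the other. This also stands and conditions the fix.

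**Conclusion.** The contradiction is certain and must be resolved before analysis. If 6.3 is followed as written, observed day-7 primary scores are dropped because of a later event, which departs from analysis of all randomised patients.

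The practical size depends on an unknown split of the attrition: 0 to about 5 of 52 patients, and 0 to about 5 percentage points of power. If excluded patients lie 10-20 mm from their arm mean, one arm's mean shifts by 0.5-2.2 mm at 5-10% exclusion. A shift of 5 mm, a third of the 15 mm target, needs every withdrawal in one arm and the larger assumed offset; the documents give no reason to expect that.

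The main reasons to act are that the analysis set is undefined and that the correction is cheap. The loss of power is secondary.

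**What to change.** Replace the exclusion sentence in section 6.3 with the 5.3 rule: all data collected up to withdrawal, including adverse events, are analysed in the arm to which the patient was randomised. State that this also applies to data already collected from patients withdrawn for further surgery.

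Then check the patient leaflet and consent form. If they carry the same rule, nothing more is needed. If participants already enrolled consented under different wording, that wording must be honoured for them, and the report should give the number affected by arm.

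The cost is a short protocol amendment and a document check, with no change to sample size, visits or data collection. It becomes more than a wording edit only if the consent documents promised exclusion.

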7. SAFETY

7.1 Potential risks & benefits to study participants

There is no anticipated personal safety risk associated with taking part in this study. If the research team learns of important new information that might affect the patient's desire to remain in the study, he or she will be told. Appropriate precautions are in place to ensure medical and personal information is kept safe through adhering to appropriate governance regulations. Any adverse events will be recorded, as outlined in sections below.

For the participants in the control group there is no direct benefit in taking part in this study. They will be cared for in exactly the same manner as they normally would. For participants in the Viscoseal intervention group, there may be benefits in terms of improved recovery and reduced pain compared to normal standard care. Although there is initial evidence that this is indeed the case, this has not yet been proven and established through a prospective randomised trial, and this study is aimed to assess this. Participants cannot claim payments, reimbursement of expenses or any other benefits or incentives for taking part in this research.

7.2 Safety definitions

Adverse Event (AE)	Any untoward medical occurrence in a patient or other clinical investigation participant taking part in a trial of a medical device, which does not necessarily have to have a causal relationship with the device under investigation.		
	An AE can therefore be any unfavourable and unintended sign (including an abnormal laboratory finding), symptom or disease temporally associated with the use of the device, whether or not considered related to the device.		
Serious Adverse Event	A serious adverse event is any untoward medical occurrence that:		
	- results in death		
	- is life-threatening		

IRAS ref 272362 Page **17** of **30**

- requires inpatient hospitalisation or prolongation of existing hospitalisation
- results in persistent or significant disability/incapacity
- consists of a congenital anomaly or birth defect.

Other 'important medical events' may also be considered serious if they jeopardise the participant or require an intervention to prevent one of the above consequences.

NOTE: The term "life-threatening" in the definition of "serious" refers to an event in which the participant was at risk of death at the time of the event; it does not refer to an event which hypothetically might have caused death if it were more severe.

7.3 Procedures for recording adverse events

All SAEs need to be reported to the sponsor/host Trust R&D within one working day of the investigator team becoming aware of them – AEs should be reported on within two weeks of becoming aware of them. For this purpose an AE report form is completed by the researcher and/or Chief Investigator

The relationship of each adverse event to the trial must be determined by the Chief Investigator, a medically qualified individual, according to the following definitions:

- Related: The adverse event follows a reasonable temporal sequence from swabbing. It cannot reasonably be attributed to any other cause.
- **Not Related**: The adverse event is probably produced by the participant's clinical state or by other modes of therapy administered to the participant.
- Severity grading: the Chief Investigator will also record if it concerns an AE or SAE.

This is recorded on the aforementioned AE reporting form. The forms are stored in the study site file.

Pseudo-anonymised copies of all adverse events forms will be shared with TRB CHEMEDICA (UK) LTD as soon as causality reporting has been performed and concluded.

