3.2 Intervention

3.2.1 Standard care (control) arm

All patients receive general anesthesia and a pneumatic tourniquet is used. Patients are already randomised prior to surgery to avoid delays with surgery and allow a vial of Viscoseal to be ready for the relevant patients. Joint irrigation is performed with the assistance of a manual arthroscopic pump using 0.9% NaCl solution at room temperature. Then, the remaining fluids are drained from the knee. At the end of the surgery, local anaesthetics is applied to the soft tissue of the arthroscopic portals [either 20 ml 0.5% Levobupivacaine (Chirocaine®), or 20 ml 0.75% Ropivocaine (Naropin®), or equivalent product], and the knee is dressed, while the tourniquet is still inflated. All surgeries are intended to be performed in a day-surgery facility with the patient being discharged the same day. Postoperatively, partial weight bearing with crutches is allowed. Crutches are recommended for the first 48 hours, primarily for patient safety by minimising the risk of a fall.

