3.2.2 Viscoseal (intervention) arm

Apart from the difference in terms of Viscoseal administration to the intervention group, the surgical protocol for the Viscoseal arm is identical to that of the standard care group. At the end of the surgery, again all the remaining fluids are drained from the knee, but this is followed by injection of 10 mL of Viscoseal preparation. Used Viscoseal product and syringes will be disposed of in line with local guidelines on disposal of clinical waste.

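### Section 7.3 ties adverse-event causality to swabbing, which is not a procedure in this trial, and its two causality classes leave out events that Viscoseal or the surgery could each explain

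*Protocol*

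**What the plan says.** Section 7.3 makes causality assessment mandatory for every event and assigns it to one role: "The relationship of each adverse event to the trial must be determined by the Chief Investigator". It then gives two classes.

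- *Related* has two conditions. The first is "The adverse event follows a reasonable temporal sequence from swabbing". The second is "It cannot reasonably be attributed to any other cause", with no guidance on how to weigh competing causes.
- The other class, *Not Related*, has a single condition: "The adverse event is probably produced by the participant's clinical state or by other modes of therapy administered to the participant".

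There is no class for possible or uncertain causality. The judgement goes on the AE form, and copies of all forms go to the manufacturer once causality has been concluded.

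Section 3.2.2 describes the exposure under test: after the joint is drained, "this is followed by injection of 10 mL of Viscoseal preparation". Section 7.2 defines an adverse event with reference to that device; it covers any "symptom or disease temporally associated with the use of the device, whether or not considered related to the device".

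Section 3.2.1 describes what both arms receive: "All patients receive general anesthesia and a pneumatic tourniquet is used", the joint is irrigated, and at the end "local anaesthetics is applied to the soft tissue of the arthroscopic portals". Section 3.2.2 says the surgical protocol is otherwise identical in the Viscoseal arm.

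**The concern.** The definition is operative text that the assessor is told to apply. Three features make it unfit as it stands.

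1. The time anchor is a procedure that the trial does not contain. It reads like text carried over from another protocol. It also disagrees with section 7.2, which uses the device as the reference point.
2. The second condition asks the assessor to rule out any other reasonable attribution. The device is given at the end of an operation with several other exposures, so timing alone cannot separate it from them.
3. The two classes are not complements. One demands the absence of a reasonable alternative. The other demands that an alternative be probable.

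At stake is the per-event causality label. It is the only place in this protocol where an individual event is judged for a link to the trial, and the manufacturer receives it.

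**Working it through.** No arithmetic applies, because the protocol states no figure on this point. The check sets the definitions side by side.

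**Step 1: the anchor.** The whole protocol was read for any swabbing procedure. The word occurs only in 7.3. Sections 3.1 and 3.2.2 give the exposure as one intra-articular instillation of Viscoseal. Section 7.2 refers to use of the device. So 7.3 conflicts with 3.2.2 and 7.2.

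**Step 2: the logic of the two classes.** For a given event, let

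- T = it follows the anchor in a reasonable time sequence;
- R = it can reasonably be attributed to another cause;
- P = it is probably due to clinical state or other therapy, with surgery and anaesthesia counted as other therapy.

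Then *Related* = T and not R, and *Not Related* = P. If P holds, R holds too, because a probable cause is a reasonable attribution. The classes therefore do not overlap. But R can hold without P: another cause can be reasonable without being probable. Any event with R true and P false falls in neither class.

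**Step 3: types of event.**

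| Event | Class, swabbing read literally (T never true) | Class, swabbing read as the Viscoseal injection |
|---|---|---|
| Surgery or clinical state is the probable cause | Not Related | Not Related |
| No reasonable explanation other than the device | None | Related |
| Device or surgery both plausible, neither probable | None | None |
| Device more likely, surgery still a reasonable explanation | None | None |

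Correcting the one word repairs the second row only. The last two rows stay unclassified because of the second condition and the word probably.

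**Step 4: are the last two rows realistic here?** General anaesthesia, tourniquet, arthroscopy with irrigation and local anaesthetic are common to all participants (3.2.1). Section 8.3 names readmission, wound-site infection, and pulmonary embolism or deep vein thrombosis for the safety overview. Section 5.5.3 has a new meniscal lesion on MRI recorded as an adverse event. Surgery or the underlying knee condition could reasonably be offered as a cause of each. *Related* is therefore hard to reach for these events, while whether the alternative is probable depends on the case.

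**Step 5: what depends on the label.** SAEs go to the sponsor within one working day and AEs within two weeks, whatever the causality (7.3). All AE forms go to the manufacturer, not only those marked related (7.3). The safety overview in 8.3 has no relatedness filter. Nothing in recording, reporting or analysis turns on the class.

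**The case against.** The best defence is that a medically qualified Chief Investigator would see swabbing as a leftover word and read it as the Viscoseal injection, since 3.2.2 and 7.2 leave no doubt about the exposure. That is likely, and it answers the claim that no event at all can be *Related*. A reader might infer a count of zero, or almost none, from the literal text. The protocol does not support a number, and an event with no surgical explanation could qualify under the sensible reading.

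A reader might also take the second condition to mean that no other cause may be possible. The text asks whether the event can *reasonably* be attributed elsewhere, which is a softer test and leaves room for judgement.

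Nor does the protocol say that unclassifiable events become *Not Related*. That class needs its own positive judgement. An assessor with only two boxes may lean that way, but a systematic shift, and hence an understatement of device harm, is not established.

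Finally, all events are captured whatever their label, and because the surgery is otherwise the same in both arms, comparing events between arms bears on device harm without using the label. This stands, and it limits the consequence. It does not make the label unnecessary. With 26 Viscoseal patients, if all were followed and none had a given event, the one-sided 95% upper bound on its rate would be 1 − 0.05^(1/26) ≈ 0.11, or about 11%. Individual assessment therefore still carries information on uncommon reactions.

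What remains after all this is a wrong anchor and two classes that do not cover every event. Reading swabbing as the injection does not close that gap.

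**Conclusion.** The point holds as an error in an operative definition with limited consequence. Section 7.3 names a procedure that is not in the trial, and its classes leave out events plausibly due to either Viscoseal or the surgery. For those events the recorded label is unreliable, because the assessor must choose a box that the definitions do not support.

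The definitions apply to every adverse event, but how many fall in the gap cannot be derived from the protocol. The conclusion assumes that the two sentences under *Related* must both be met, and that surgery and anaesthesia count as other therapy. If they did not, still fewer events would meet *Not Related* and the gap would be wider.

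The documents do not support reading this as a failure of safety surveillance. Recording and reporting of AEs and SAEs, sharing of forms and the descriptive safety overview are unaffected. The correction should be made, but the point does not threaten the primary result.

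**What to change.** - Reconcile 7.3 with 3.2.2 and 7.2: replace swabbing with the instillation of Viscoseal (use of the device) or another trial procedure.
- Make the two classes exhaustive and mutually exclusive. One way is to define *Related* as a reasonable possibility that the device or a trial procedure caused or contributed to the event, and *Not Related* as no such reasonable possibility. Other wording would serve if every event falls in exactly one class.
- Check that the AE form uses the same wording. The form is not part of the protocol, so whether it repeats the error is unknown.
- Re-assess any event already classified under the current text, keeping the earlier label on file.

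The cost is a wording amendment, possibly a revised form, and the time to review events already assessed. The count of related events may rise, and a report should say that this reflects the changed definition. Treatment, visits, sample size and the efficacy analysis are untouched.

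### Section 7.3 defines adverse-event severity grading as AE or SAE, which is seriousness, so the stated rule never grades the intensity of non-serious events

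*Protocol*

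**What the plan says.** Protocol section 7.3 lists what the Chief Investigator determines for each adverse event. After the two relatedness categories comes: "Severity grading: the Chief Investigator will also record if it concerns an AE or SAE". The next line adds: "This is recorded on the aforementioned AE reporting form". Section 7.3 describes no other grading item. The same section sets the reporting times (one working day for SAEs, two weeks for AEs) and says that pseudo-anonymised copies of the AE forms go to the manufacturer.

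Section 7.2 fixes what AE and SAE mean. Its definition opens "A serious adverse event is any untoward medical occurrence that" and continues with a list of consequences: death, threat to life, admission or a longer stay, lasting or significant disability, and congenital anomaly. The admission criterion reads "requires inpatient hospitalisation or prolongation of existing hospitalisation". Other important medical events "may also be considered serious if they jeopardise the participant or require an intervention to prevent one of the above consequences". A note on the life-threatening criterion says that "it does not refer to an event which hypothetically might have caused death if it were more severe".

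Section 8.3 plans a descriptive safety overview to 26 weeks. It covers return to theatre or hospital, wound infection, and pulmonary embolism or deep vein thrombosis. It does not use a severity grade.

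**The concern.** Seriousness and severity are different properties of an event. Seriousness is about consequence and drives expedited reporting. Severity is about intensity. An event can be intense without being serious, and serious without being intense. Section 7.3 announces the second and then records the first.

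The product is instilled into the joint. The local reactions one would want to describe, such as pain, swelling or stiffness of the operated knee, would often meet none of the 7.2 criteria. Under the stated rule they all become 'AE', with nothing to separate a trivial reaction from an intense one. Intensity that is not recorded when the event is reported cannot be reconstructed later, so this is not a detail that an analysis plan could supply.

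**Working it through.** No arithmetic is needed for the main point. It follows from setting 7.3 beside 7.2.

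**Step 1. What the field can contain.** By 7.3 the field has two values, AE and SAE.

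**Step 2. What decides the value.** By 7.2 an event is an SAE if it meets a listed consequence, or if it is judged an important medical event because of jeopardy or the need for an intervention. None of these is a threshold on intensity. The note on life-threatening events points the same way, since it keeps the serious criterion apart from how severe the event might have been. It clarifies that one criterion only and sets no general rule.

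**Step 3. Cross intensity with seriousness.**

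| Event | Meets a 7.2 criterion? | Value recorded as severity |
|---|---|---|
| Mild | No | AE |
| Severe | No | AE |
| Mild | Yes | SAE |
| Severe | Yes | SAE |

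The recorded value depends only on the middle column. All non-serious events share one value. If no SAE occurs, the field is constant for the whole trial. The protocol gives no expected SAE rate for its 26 patients per arm, so how close to constant it would be cannot be calculated.

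**Step 4. Is intensity graded anywhere else in the AE record?** Not in the protocol text. The none/mild/moderate/severe columns in Appendix 1 belong to the patient-completed short-form McGill questionnaire and do not grade adverse events. The AE form itself is not reproduced.

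**Step 5. What do the scheduled outcomes cover?** Table 2 in section 5.5.2 gives, after surgery:

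- rest pain on the VDS at 48 hours, 7 days, 14 days, 12 weeks and 26 weeks;
- McGill at 48 hours, 7 days and 14 days;
- limb girth at 14 days and 12 weeks (section 8.3 instead names 7 and 14 days);
- Lysholm, WOMET and walking pain at 12 and 26 weeks;
- analgesic and anti-inflammatory use at every time point.

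The VDS question in Appendix 1 asks about the last 2 days. At nominal times, the five rest-pain ratings therefore cover 5 × 2 = 10 days of a follow-up of 26 × 7 = 182 days, and 10/182 = 5.5%. Nominal gaps include days 2 to 5, days 7 to 12, and most of the time from day 14 to week 12. Adverse events are asked about at each follow-up contact (section 5.4), so the AE record is where a reaction in a gap would appear. Stiffness has no graded early measure in Table 2: the function scales start at 12 weeks.

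**The case against.** The strongest reply is that this is a labelling slip with little consequence. Much of that stands.

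- **Pain and swelling are already compared by arm.** A reader might infer that the trial cannot show whether knee reactions were worse with Viscoseal. The protocol does not support that. Pain at rest on day 7 is the primary outcome, pain and girth are measured in both arms, and for these two symptoms the scales tell more than a three-level tick-box. The remaining loss is event-level intensity between assessments, and early stiffness.
- **Nothing downstream uses the wrong label.** A reader might infer that safety reporting is compromised. It is not: the reporting times depend on seriousness, which is the right trigger, and section 8.3 plans no table by severity.
- **An inverted ranking is possible, not automatic.** A reader might infer that an intense reaction managed at home always ranks below a mild event with an overnight stay. The first could still be an SAE through the important-medical-event clause or the disability criterion. The second requires a judgement that the event needed admission. Section 3.2.1 says only that "All surgeries are intended to be performed in a day-surgery facility with the patient being discharged the same day", which is an intention. Neither route is an intensity rule, so the field still does not measure intensity.
- **The form is not shown.** A reader might infer that the manufacturer receives forms with a mislabelled severity field. The form may already grade each event. Only the protocol text can be judged, and it describes no such item.

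It can also be said that renaming the item cures the stated error and that an intensity scale is a preference. Renaming does cure the contradiction. But 7.3 sets out to grade severity, and renaming alone would leave that undone.

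**Conclusion.** The point holds as an error in the text. Section 7.3 defines severity grading by a split that section 7.2 defines as seriousness, so the stated rule does not grade severity and gives every non-serious event the same value. The loss is confined to the intensity of individual non-serious events in the AE record, mainly local knee reactions between scheduled assessments and early stiffness. The between-arm comparison of pain and swelling at scheduled times and the handling of SAEs are unaffected.

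This rests on the AE form following the protocol text. If the form already has an intensity field, only the wording of 7.3 needs correcting. Priority is minor to moderate: the harm is limited, but what is lost cannot be recovered later and the correction is cheap.

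**What to change.** In section 7.3, rename the AE/SAE item 'Seriousness (by the 7.2 criteria)'. Add a separate item, 'Severity: mild, moderate or severe, by effect on usual activities', and put the matching field on the AE form if it is not already there. Then describe adverse events by arm using both.

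The cost is one sentence in 7.3 and one extra tick-box per event, with no added visits or staff. The same amendment could correct the neighbouring relatedness definition, which times events from swabbing, a procedure that the protocol describes nowhere else.
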